All tools are hand washable and will belong to the patient (will not be used between patients). Tools include the circle tool (yellow), bar tool (blue), L tool (green). See Appendix G for proposed placements.

This study will be conducted as a single-subject design. Each patient will serve as his/her own control based on the purpose of the study and the large heterogeneity among patients. Conditions which would result in participant exiting the study might include: non-compliance, subject withdrawal of consent, unexpected need for additional surgeries during the treatment period.

Proposed data points (see below) were adapted from the study completed by Hadlock and Urban [7]. In their 2012 study, they assessed resting facial distance relationships and changes in these relationships during movements to form different facial expressions using a novel device called Facial Assessment by Computer Evaluation (FACE). The creators of the Easy Stretch Toolkit will use UTMB customized facial measurement software designed for this study to measure pre- and post-use change. See Appendix K. The specific measurements to be taken during selected facial movements are discussed below.

4. Study Procedures:

Protocol

In this initial pilot study, we will recruit 20 adult or pediatric patients who have sustained facial burns or who have sustained a facial injury. A facial injury can be any disorder that results in scarring, tightness, limited range of motion of facial skin or musculature or fibrosis. For the purpose of this study, facial burn injury or facial injury will be defined as an injury to the midface or lower half of the face and may be unilateral or bilateral. Participants must be in the chronic phase of recovery to complete the 8 week treatment. Chronic burns are defined as those burns that are not in the acute

[name] and [name]

Version 10/October 2020

Page 5 of 24

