healing phase, ie., there are no concerns for injury to new or healing skin or wound dehiscence. A 20 subject sample size can generate meaningful estimates for the change and its variation, and within the range that sample size is recommended for feasibility study based the consideration in gain of precision for each increase of 1 in sample size [13]. Participants will need to be able to complete the entire 2 month prescriptive program. All participants will need to be able to attend weekly visits via in person or electronic means (telehealth) such as Skype, Zoom or other electronic platform for an enrollment screening, followed by a total of 8 weeks of treatment. Pediatric participants will need consent from a caregiver who will commit to being present for all in person or electronic visits as well. Participants who are referred to the study will be contacted via phone to determine eligibility criteria. If the participant meets eligibility requirements and selects telehealth option, a copy of the written consent form will be emailed to the participant. Verbal consent will then be obtained for enrollment in the study and background information will be obtained for the case history form. A package will be mailed to the participant including a full set of tools, a pupil distance eye ruler, copy of the consent form, written subject handouts including pages for weekly documentation of use of the tools, and return envelopes for homework and tools. If the subject lives locally and wishes to be seen at a UTMB clinic or their place of residence, visits may be done in person as well. Telehealth option is available for all study participants, ages 7 and up.

In cases of verbal consent, the investigators will request verbal confirmation by the subject/parent that they signed and dated the written consent form. If unable to print the consent/assent/permission, the subject/parent will sign and date a blank piece of paper with a written statement that they voluntarily agree to participate in the protocol. This statement will include the protocol number and name (Easy Stretch Toolkit, #18-0005). After signing and dating the newly created document, the study participant or legally authorized representative will send a photograph of the signed and dated statement or consent form by fax, text message or email to the investigator/designee or may return the document by mail at a later date. In all cases, informed consent will be obtained prior to participation in the trial.

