After informed consent by the subject and parent/caregiver (if applicable), each subject will complete an initial assessment during which the Speech Pathologist will select the appropriate tool(s) from the Easy Stretch Toolkit and provide training to the subject and/or caregivers in use of the device(s). During each visit, the Speech Pathologists will select the desired tools from the Toolkit and their accompanying oral placement. The recommended photographs of the 9 facial expressions will be taken via screen shots. Education will be provided regarding tool selection and placement location during each weekly visit. Participants will need to return their homework sheets and self-made photographs of each facial expression via email to the Speech Pathologists each week or by mail at the end of the study period.

The tools are available in small, medium and large sizes. The small to medium sizes for each shape should be the correct size for children's mouths. Subjects and caregivers (may be parent or guardian, in the case of pediatric population) will be trained until they can demonstrate independent carryover of the placement and verbal confirmation of the prescribed protocol. See attachment for patient/caregiver education materials to be used, which will include written instructions for the patient (Appendix I). Data to be gathered includes pupil distance, VROM, HROM and facial measurements at rest and while the subject is completing specific facial movements, with goal of demonstrating increased range of motion of the oral musculature and improved facial and scar appearance over time (Appendix H). Initially it will be proposed that the chosen head shape be used [name] and [name]
Version 10/October 2020
Page 6 of 24

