for 60 minutes (+/- 10 minutes) 2 times per day for each day of the study. Frequency of use of the device will be closely documented by the Speech Pathologists and the patient or caregiver using the provided charting system (Appendix I). Because use of the devices will be prescriptive, the applicable head shape(s) and placement(s) will vary by individual and by week. Specifically, placement(s) is (are) expected to vary each week based on the clinical needs of the subject and outcomes seen from the prior week's intervention. For monitoring purposes, data will be gathered at the initial assessment and 1 time per week thereafter (+/- 2 days) for the duration of the 8 week trial. As a result, data will be evaluated as to the prescriptive plan for deficits for specific facial landmarks and their associated muscle groups (cheeks, nasolabial folds, upper lip, mentolabial junction and modiolus). Subject safety will be met via an initial training session and weekly one-on-one follow-up visits via FaceTime, Skype or in person visit with the monitoring Speech Pathologist to assure appropriate use of the devices. Patient (or parent) handouts (Appendix I) will be provided to assist with recording of time spent using the devices and with which tool and placement location.

Assessment of the patient after completion of informed consent

- Photograph of the patient's face from the front, as well as their side profile (weekly), with measurements taken from the photograph at specific points. At this time, profile photographs will not be used for measurements or analysis but will be kept to show visual changes over time.
- Oral-motor facial examination will be conducted.

Targeted muscle groups [8]

The facial muscles to be targeted include:

- Levator labii superioris – elevates the upper lip and deepens nasolabial furrow
- Buccinator – controls movement of the cheeks and assists in sucking in neonates and mastication in pediatrics and adults
- Depressor anguli oris – assists with frowning, pulls corner of mouth inferiorly
- Mentalis – protrudes lower lip, inward and upward movement of the soft tissue of the chin
- Zygomaticus major – pulls angle of mouth upward and laterally
- Zygomaticus minor – raises upper lip
- Nasalis – compresses bridge, depresses tip of nose, elevates corners of nostrils
- Levator anguli oris – assists with smiling, elevates angle of the mouth
- Depressor septi – depression of the nasal septum

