The customized UTMB facial software is a two dimensional measurement system. Jorge Jr., et al, provided a summary of several past and present measurement systems, considered as subjective vs objective and simple vs complex, in their article exploring measurement of peripheral facial paralysis [9]. Although a three dimensional measurement system such as the Vicon system [9] is beneficial for quantifying measurements across multiple axes especially the anteroposterior axis, the creators chose to pursue a two dimensional measurement system for its cost effectiveness and ease of use. The UTMB customized facial software is based upon use of pupil distance, as this is a static landmark and subsequent measurements can be graded based on this measurement. Fields and Peckitt performed a similar measurement in their study, called the Facial Nerve Functional Index, measuring percentage change from the corner of the lip with a mouth closed position to the external corner of the ipsilateral eye vs smiling broadly [9]. In their 2015 article on use of their 3D dynamic quantitative analysis system of facial motion (3D ASFM) and assessment of mimic muscles during facial contraction, Feng et al proposed that the mouth-eye association and their related movements have the greatest influence on quality of life [10].

Endpoints include degree of excursion during different facial movements. Description of change will be documented in degree of difference in millimeters of movement when producing each expression with subsequent statistical analysis to determine that mean changes and variation of changes, and if

change was not the result of chance. Multiple studies have attempted to define a “normal” range of motion [9,11]. Specifically, although facial landmarks are consistent, it must be considered that there are differences in facial expressions and excursions within the same individual for both sides of the face, as well as between individuals of different races, ages and gender [9]. For this reason, the creators are unable to predict a percent change as there are currently no consistent norms for range of motion and excursions of facial landmarks. Therefore, change will be evaluated within a single subject over completion of the course of treatment.

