Expected benefits include: increasing range of motion for multiple facial muscles and tissues; reducing the impact and appearance of scar tissue; ability to target multiple sites across the face, with particular attention to the cheeks, nasolabial folds, upper lip, mentolabial junction and modiolus; achieving a stretch that currently available tools cannot provide; improved ability to produce different facial expressions; increased speech intelligibility; improved ability to complete oral hygiene.

14. Biostatistics:

Sample size calculation shows that a sample size of 20 (accounting for 10% missing rate) will be able to detect an effect size of 0.7 by using a two-sided paired t-test, if the real study has statistical power of 0.8 and the significance level (alpha) is 0.050.

Descriptive statistics for continuous and categorical variables will be presented as mean \pm SD and quartiles, and frequencies and proportions, respectively. For the weekly measurements, we will use the descriptive statistics and individual trend plots to present the data. The primary outcome is the change in millimeters after the completion of treatment (post – pre measures) for each facial expression. We will use paired t-tests (if data is normally distributed) or non-parametric alternatives (e.g., Wilcoxon signed-rank test) to test if the changes are statistically significant. The change score of facial disability index (FDI) will be analyzed using the same method. The pre-post outcome of the cranial nerve assessment will be classified by categories (Pass-

Pass, Fail-Pass, Fail-Fail), and the frequencies and proportions will be reported. Two-sided statistical significance will be considered for alpha at the 0.05 level for all tests.

References:

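### Single-subject label without a baseline phase: one pre-treatment measurement cannot show whether an individual's change exceeds session variation, and no change can be attributed to the device rather than practice or time

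*Combined protocol and SAP*

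**What the plan says.** Section 3 (Concise Summary of Project): "This study will be conducted as a single-subject design". The next sentence reads "Each patient will serve as his/her own control" and gives as reasons the study's purpose and how much patients differ. Section 4, Measuring Outcomes, adds that "change will be evaluated within a single subject over completion of the course of treatment".

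The schedule is in Section 4. Participants attend "for an enrollment screening, followed by a total of 8 weeks of treatment". No facial measurement is described at the screening. Then "each subject will complete an initial assessment during which the Speech Pathologist will select the appropriate tool(s) from the Easy Stretch Toolkit", and training takes place at that same visit. On timing, "data will be gathered at the initial assessment and 1 time per week thereafter (+/- 2 days" either way, through week 8. The section on recruitment and consent has participants start straight away, and Section 4 has the device used daily throughout. No lead-in, withdrawal phase or control group is described.

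Section 14 defines the primary outcome as post minus pre in millimetres for each expression. The test is for the group: "We will use paired t-tests (if data is normally distributed", otherwise a signed-rank test. Weekly measurements get descriptive statistics and individual trend plots. There is no within-person test, no threshold for individual change and no estimate of measurement repeatability.

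**The concern.** A single-subject design normally rests on repeated observation before treatment, so that each person's untreated level and variability are known. Here there is one untreated value per person. Two questions then have no planned answer.

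- **For one person:** is a gain of some millimetres larger than the difference between two ordinary sessions of posing the same expression? The software was made for this study, and the text gives no repeatability figure for it.
- **For anyone, singly or as a group:** is the gain due to the device? Participants pose the same nine expressions every week and also send in their own photographs. Any improvement from rehearsal, familiarity with the camera or the passage of time enters post minus pre and is counted as device effect. The blinded observer guards against rater bias, not against this.

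Aim 1 asks whether using the devices changes range of motion, and Section 2 plans to power a larger trial from the effect sizes seen here. Drift would be carried into those effect sizes.

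**Working it through.** **Inputs.** From Section 14: N = 20, 10% missing (20 x 0.9 = 18 evaluable), effect size d = 0.7 (mean change / SD of change), two-sided alpha 0.05, power 0.80. From Section 4: one initial and eight weekly measurements, so nine points per person. Not in the documents, and so assumed: the drift unrelated to the device, and the share f of the change variance that is session noise. Write s for the within-person session SD.

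**1. The plan's own figure.** The paired t-test with n = 18 has noncentrality d x sqrt(18). At d = 0.7, exact power is 0.799, so the stated sample size reproduces.

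**2. Random session noise and the group test.** With zero true change, independent noise at pre and post, and n = 18, the simulated rejection rate over 200,000 runs was 0.049 against a nominal 0.05. Session noise is already in the SD of the paired differences, so the test keeps its error rate.

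**3. Systematic drift and the group test.** With no device effect, put the drift in place of d in the power formula of step 1 (n = 18):

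| Assumed drift (SD of change) | Chance of p < 0.05, per expression |
|---|---|
| 0.2 | 0.126 |
| 0.3 | 0.225 |
| 0.5 | 0.516 |

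**4. One person's change.** With one pre and one post value the noise variance is 2s², so the 95% limit is 1.96 x sqrt(2) x s = 2.77s. With the mean of two pre values and one post value it is s²(1/2 + 1) = 1.5s², and the limit is 1.96 x sqrt(1.5) x s = 2.40s. Both limits treat s as known, and the plan does not estimate it.

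**5. What the weekly data could give.** A straight line through nine weekly points has Sxx = 60. The fitted 8-week change has standard error 8s/sqrt(60), and its 95% limit on 7 degrees of freedom is 2.365 x 8s/sqrt(60) = 2.44s, with s estimated from the residuals. The plan does not specify this analysis, and the slope would still mix practice with device effect.

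**6. Effect of a second baseline.** If the noise in the two baselines is independent, averaging them multiplies the change variance by v = 1 - f/4. The effect size becomes 0.7/sqrt(v), and a drift fixed in millimetres becomes drift/sqrt(v):

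| f (assumed) | v | Effect size | Power, n = 18 | Rejection at drift 0.2 / 0.3 / 0.5, no device effect |
|---|---|---|---|---|
| 0 (as planned) | 1 | 0.700 | 0.80 | 13% / 22% / 52% |
| 0.25 | 0.9375 | 0.723 | 0.82 | 13% / 24% / 54% |
| 0.5 | 0.875 | 0.748 | 0.85 | 14% / 25% / 57% |
| 1 | 0.75 | 0.808 | 0.90 | 15% / 28% / 64% |

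The drift columns ignore any practice gain between the two baselines, of which the mean would absorb half.

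**The case against.** **Own control may mean only that no norms exist.** The Section 4 sentence on single-subject change follows an explanation that no consistent norms for facial excursion exist, and Section 3 cites heterogeneity. On that reading the plan promises only comparison with the patient's own start, which a paired test provides. This is fair. It narrows the point to a label that claims more than the design supports, but it supplies neither a within-person rule nor a way to separate practice.

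**Individual change is not beyond reach.** A reader might infer that no individual's change could ever be judged. The documents do not support that: nine weekly points per person could yield a within-person SD (step 5). The gap is an unspecified analysis, not a lack of data.

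**Session noise does not spoil the group result.** A reader might also infer that the group change cannot be told from session noise. Step 2 shows otherwise.

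**A second baseline does not cure practice.** Two sets taken days apart cannot show what eight weeks of rehearsal does, so they are not a no-treatment comparison for the 8-week change. The smaller SD also makes the test somewhat more likely to reject under a fixed drift (step 6). This stands in full and limits what the fix can claim.

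**Feasibility differs by route.** Photographs need prior consent, and consent may come at the start of the first treatment session. In-person participants may therefore have no earlier contact at which to be photographed. This also stands. The wait for the mailed kit, after consent, exists only for telehealth participants.

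**It is a pilot.** An uncontrolled pre-post design is a legitimate choice for a first study. The lack of a control arm is not the fault raised here.

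**Conclusion.** The point holds with limits. The single-subject label has no baseline phase or within-person rule behind it. Under the planned analysis an individual's change cannot be told from session variation, and neither individual nor group change can be attributed to the device rather than to practice or time. The group test remains valid as a test of whether mean change is zero; what it cannot do is assign the cause.

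The size depends on quantities the documents do not give. A drift of 0.2 to 0.5 SD of change would produce a significant result in 13% to 52% of trials of a useless device, per expression. A second baseline would add 2 to 10 percentage points of power for noise shares of 25% to 100%. Both ranges are assumptions, and the power gain also assumes independent noise at the two baselines. The absence of repeatability data is confirmed only for the text available, because the software example in Appendix K could not be seen.

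This is a cheap improvement worth making, not a defect that invalidates the pilot.

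**What to change.** **Measurement.** After consent and before first device use, take the nine-expression photo set twice.

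- Use separate days wherever consent precedes the initial assessment, for example while telehealth participants wait for the kit. The pupil ruler comes in that kit, but Section 4 treats pupil distance as static, so earlier photographs can be scaled afterwards.
- Otherwise take both sets at the initial assessment and report the result as within-session repeatability only. Noise shared by the whole session is then not averaged out, and the power gain is smaller than in step 6.
- Have the same blinded observer measure both sets in shuffled order.

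**Analysis (Section 14).**

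- Use the mean of the two sets as the pre value in the paired test.
- Report the within-person SD from the separate-day baselines or from residuals around each person's weekly trend.
- Judge individual change against 2.40 times that SD. The multiplier 2.77 applies only to one pre and one post value.
- Report the shift between the two baselines only as a check for early familiarisation.

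**Description.** Replace the single-subject label with uncontrolled pre-post pilot, and state that the observed change cannot be separated from eight weeks of practice.

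**Cost.** A few minutes of photographs and some observer time per participant, a short addition to Section 14, and no new staff. No extra visit is needed if in-person participants have both sets taken at the initial assessment. The drawback is that a smaller SD also makes the test more sensitive to any practice drift, so the change of description is needed alongside the second set.

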- Risorius – draws back the angle of the mouth laterally
- Depressor labii inferioris – depression of the lower lip
- Obicularis oris – sphincter around the mouth, brings lips together, retracts lower lip

Measuring Outcomes

The investigators will use photographs of the patient to measure multiple facial features and excursions during movement. Required materials include: a set of the Easy Stretch devices, departmental iPad with iPad stand or access to personal computer or smartphone, UTMB customized facial measurement software, computer, CEN-TECH 6" digital caliper.

Pictures will be taken with the patients in a seated position and head in neutral and midline position. Subjects will be asked to take photos with their eyes open and their face fully within the frame. A single blinded observer will be used to complete the measurements taken in the facial measurement system.

Measurements to be taken:

- Pupil distance
- Horizontal distance between outside of nares
- Pupil to outside of nares (right and left)
- Pupil to outside corner of lip (right and left)
- Superior edge of philtrum to outside corner of lip (right and left)
- Nares to outside corner of mouth (left and right)
- Length of philtrum
- Superior border of upper lip to inferior border of lower lip
- Horizontal distance between outside corners of lips
- Inferior border of lower lip to inferior tip of chin

Measurements will be taken during each of the following targeted facial expressions:

- At rest
- Wrinkle the nose
- Gentle smile
- Broad smile with lips closed
- Broad smile with teeth together
- Vocalizing prolonged “eee” sound
- Vocalizing prolonged “ooo” sound
- Lip pucker
- Mouth opening as measured by distance between inferior upper lip and superior lower lip

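### Photographs are not timed relative to device use, so an immediate effect of stretching could not be separated from change over the 8-week course

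*Combined protocol and SAP*

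**What the plan says.** **Use of the device.** Section 4 (Study Procedures) proposes, as a starting regimen, that the chosen head shape be used "for 60 minutes (+/- 10 minutes) 2 times per day for each day of the study". Head shapes and placements may then vary by person and week.

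**Timing of assessments.** In the same section, "data will be gathered at the initial assessment and 1 time per week thereafter (+/- 2 days"). This limits the day of the visit. It does not set the hour or the time since the device was last used.

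**Standardisation of photographs.** Under Measuring Outcomes: "Pictures will be taken with the patients in a seated position and head in neutral and midline position". Eyes open and full framing of the face are also required. Nothing is said about recent stretching.

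**Order within a visit.** Section 4 places tool selection and training within the initial assessment, and teaching on tool choice and placement within each weekly visit. It does not say whether the photographs come first. Participants also send in photographs they take themselves, with no timing rule.

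**Analysis.** Section 14 (Biostatistics) defines the primary outcome as the post minus pre change in millimetres for each expression once treatment is complete. A paired t-test or a non-parametric alternative is applied. No interval after the last session is given, and no later visit off treatment is planned.

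**Records.** Appendix H records the date and time of the assessment. Appendix I records minutes of use by date, in AM and PM columns, without clock times.

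**The concern.** The primary contrast compares a photograph taken before the course with one taken at its end. If the final photograph may be taken minutes after an hour of stretching in one participant and many hours after in another, any short-lived response of the tissue becomes part of the measured change. It would fall mainly on the post side, because the baseline precedes the twice-daily sessions.

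Three features leave it uncorrected. Each participant is his or her own control (Section 3), so no concurrent arm would cancel it. The single blinded observer measures the face in the photograph, and the effect would be in that face. The interval cannot be reliably reconstructed afterwards, because Appendix I holds no clock times.

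The plan's stated interest is change across the course of treatment and an effective 8-week rehabilitation plan. Section 2 also says that effect sizes will inform the power analysis of a larger trial, so a contaminated estimate would carry forward. Uneven timing would also add noise to the weekly trend plots. The Facial Disability Index is less exposed, since its Part 2 asks about the past month.

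**Working it through.** **Inputs from the documents (Section 14).** "a sample size of 20 (accounting for 10% missing rate"), hence 20 × 0.9 = 18 evaluable; "effect size of 0.7 by using a two-sided paired t-test"; "statistical power of 0.8 and the significance level (alpha) is 0.050".

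**Input not in the documents.** The size of any immediate effect of stretching, written τ, in units of the SD of the change score. It is assumed, and a range is shown.

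**Step 1: reproduce the plan's figure.** For a two-sided paired t-test with n pairs and standardised mean change d, the statistic follows a noncentral t distribution with n − 1 degrees of freedom and noncentrality d√n. With n = 18 and d = 0.7, the noncentrality is 0.7 × √18 = 2.97 and the critical value on 17 df is 2.11. Power is 0.799, which agrees with the stated 0.8. The effect detectable with power 0.8 at n = 18 is 0.701. The plan's figure is reproduced, and the same formula can be used for the illustration.

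**Step 2: no change over the course, average shift τ at the final photograph.** Put d = τ, taken in the direction counted as benefit. Results are for one expression.

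| Average shift τ (SD of change) | Noncentrality τ√18 | P(p<0.05) | of which in the benefit direction |
|---|---|---|---|
| 0 | 0 | 0.050 | 0.025 |
| 0.1 | 0.42 | 0.069 | 0.059 |
| 0.2 | 0.85 | 0.126 | 0.123 |
| 0.3 | 1.27 | 0.225 | 0.224 |

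**Step 3: mixed timing.** Suppose each final photograph has an even chance of closely following a session, and the effect has gone in the rest. By simulation (200,000 trials of 18), a shift in the exposed photographs of 0.3, 0.5 or 0.7 SD gives P(p<0.05) of about 0.09, 0.16 or 0.26. The average shifts are half of these: 0.15, 0.25 and 0.35 SD. What matters is mainly the average across participants, which depends on both the effect and how often photographs follow a session closely. The plan controls neither.

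**Step 4: can the records recover the interval?** Appendix H gives the clock time of the assessment. Appendix I gives minutes per half-day. For a visit at midday with minutes entered under AM, the session could have ended just before the visit or several hours earlier. The two forms often show whether a session came before the visit, but not how long before.

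**The case against.** The strongest case against runs as follows.

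- **The baseline may not be device-free.** A reader might infer that baseline photographs have never seen the device. The text does not support this: participants are trained at the initial assessment until they can place the tools independently, and the order relative to the photographs is not stated. A baseline photograph taken after training would offset part of the effect. This stands, and it is a second gap of the same kind.
- **The sign is unknown.** A reader might infer bias towards benefit. The documents report no immediate effect in either direction. Several distances are measured in each of nine expressions, and improvement is not always more millimetres; a better pucker, for instance, would bring the lip corners together. Section 10 lists discomfort and asymmetrical movement as possible effects of stretching, and these could reduce excursion. This stands: the direction in the table is an assumption.
- **Final photographs need not follow same-day use.** The twice-daily schedule is an initial proposal, and Section 14 places the final measure once treatment is complete. So same-day use is possible but not established. The point needs only that the plan permits it.
- **Large shifts are strained.** An average of 0.5 SD would give p<0.05 in about 52% of trials. If only half the final photographs were exposed, it would need 0.5 / 0.5 = 1.0 SD in those, more than the 0.7 the study is sized to detect. The documents do not support relying on that figure.
- **The forms may help.** Appendix H lists the pictures before the next placement, which suggests an order without requiring one. The complete forms and education materials are separate documents not available here, so a timing instruction there cannot be excluded.
- **This is an uncontrolled pilot**, and the primary outcome is not described as lasting. That tempers the severity. It does not remove the ambiguity in what post minus pre measures.

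**Conclusion.** The point holds as a gap in measurement timing. The plan permits final photographs soon after a session and does not fix the order of photographs and training at baseline. An immediate effect of stretching, if there is one, would be mixed into the primary outcome and could not be separated from change over the course.

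Its size is unknown. Under the assumption of an average shift of 0.1 to 0.3 SD of change in the benefit direction, 18 evaluable participants and no change over the course, the chance of p<0.05 on one expression is about 7% to 22%, against a nominal 5%. These figures show how sensitive the test is to such a shift. They do not estimate the bias in this trial. The sample size calculation is unaffected.

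The point is worth correcting even in a pilot, because the remedy is cheap and the interval cannot be reliably recovered after the data are collected.

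**What to change.** In Section 4, including Measuring Outcomes, and in Appendix H:

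1. Take baseline photographs before any tool placement or training.
2. At every later visit, take photographs before any placement teaching and, where the visit can be booked that way, before that day's first use.
3. Add a field to Appendix H for the clock time of last use.
4. In Section 14, add a sensitivity analysis that repeats the primary analysis without final photographs taken after same-day use.

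The prescribed frequency and duration of use are not changed. Where a visit cannot be booked before the day's first use, the photograph is still taken and the recorded time identifies it.

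The cost is a few sentences and one form field. The small downsides are constraints on booking visits and, in the sensitivity analysis, fewer than the roughly 18 evaluable participants, so its result should be read as a check on direction and size rather than as a second test.
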